7.5 Analysis of Secondary Outcomes

Secondary Aims I

Individuals in the active arm with Impel device will demonstrate slower rate of decline on secondary outcomes including CDR-SB, memory composite (Story Recall and FCSRT), and ADCS-ADL MCI in comparison to the placebo arm. Mixed Model repeated measures (MMRM) models similar to the primary analysis will be used.

Secondary Aims V

To determine whether further improvement occurs after 18 months of treatment.

- The analysis will be the same as the primary analysis with data up to the month 18. The null hypothesis is that the treatment difference between active and placebo with Impel device for the ADAS-Cog12 at month 18 is equal to zero.
- Delayed-start analysis is to compare Δ_2 , the treatment differences between active and placebo at the month 18 (delayed-start period) with Δ_1 that at the end of the placebo-controlled period with noninferiority margin as 50% of Δ_1 [1, 2].

7.6 Analysis of Safety Outcomes

To assess the safety and tolerability of treatment with INI over a 12 month compared to placebo. Tolerability and safety will be determined by serious adverse events, adverse events and treatment discontinuation rate of INI/placebo as determined by the participant and the physician. AEs and SAEs will be recorded and categorized by body system, event type, attribution, frequency, severity, and course. Differences for rates of AEs, SAEs or other abnormalities between groups will be assessed using Fisher's Exact tests. Changes in vital signs, and laboratory tests between groups will be assessed using a MMRM approach analogous to the primary analysis.

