### 3.8 Safety and Compliance

No treatment-related serious adverse events (SAEs) occurred during the study; most adverse events (AEs) were minor, such as mild rhinitis. AEs with an occurrence of >5% in any group are listed in Table 3. The total AE mean was higher for the low dose group compared with placebo (low dose mean total AEs with standard error=1.44±0.20, placebo =0.80±.22, p=0.04), with a similar trend for the high dose and placebo group comparison (high dose mean total AEs =1.21±0.16, placebo =0.80±.22, p=0.10). Mean compliance (number of completed doses) ranged from 95-97% and did not differ across groups.

**Table 3 | Total number of adverse events and percent of sample for all events occurring for at least 5% of the participants in any treatment group.**

	Placebo	Low Insulin	High Insulin
Total AEs	27/56.7%	55 * /72.2%	51 + /68.4%
Dizziness	3/10%	3/8.3%	5/13.2%
Headache	1/3.3%	4/8.3%	2/5.3%
Nose bleed	0/0.0%	6/8.3%	3/2.6%
Rhinitis	1/3.3%	8/16.7%	4/7.9%
URI	2/6.7%	2/5.6%	1/2.6%
Fall	2/6.7%	1/2.8%	1/2.6%
Rash	2/6.7%	1/2.8%	2/2.6%
Other	16/46.7%	30/58.3%	33/60.5%

\* Low Insulin Total AEs > Placebo, p<0.05

+High Insulin Total AEs > Placebo, p<0.10

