## **6.0 STUDY TIMELINE**

The approximate timeline for this four-year study is projected as follows: 1) approximately six months for study startup activities including FDA/IND submission, site IRB and regulatory approvals and the Investigator training meeting; 2) recruitment will last for approximately 18 months (for a total of 240-300 participants across about 30 sites); and 3) 18 months of follow up (last 6 months are open label)

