The application of the ITT principle in a change score analysis requires the imputation of any missing “post” observations. A multiple imputation strategy will be utilized for missing endpoints. Missing post-baseline data will be imputed via multiple imputations from the general location model (Little and Rubin 1987). Point estimates, standard errors, confidence intervals, and p-values will be computed using standard inference procedures for multiple imputations (Little and Rubin 1987). Safety data will be analyzed using exact contingency table methods by study arms. AEs will also be *subcategorized by relationship to study drug (unrelated/possibly related/probably related)*. Details of the analytic models will be stated in a formal statistical analysis plan (SAP) that will be generated and finalized within six months of anticipated data lock.

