## 16.0 ADVERSE EVENTS

### 16.1 Definition

An adverse event (AE) is defined as per the Code of Federal Regulation Title 21 Part 312.

<http://www.accessdata.fda.gov/scripts/cdrh/cfdocs/cfcfr/cfrsearch.cfm?fr=312.32>

Adverse events which occur after informed consent is signed include but are not limited to: (1) worsening or change in nature, severity, or frequency of conditions or symptoms present at the start of the study; (2) participant deterioration due to primary illness; (3) intercurrent illness; and (4) drug interaction. An abnormal laboratory value will only be reported as an AE if the investigator considers it to be an AE, or if it leads to the participant being withdrawn from the study.

The investigator should attempt to establish a diagnosis of the event based on signs, symptoms, and or other clinical information. In such cases, the diagnosis should be documented as the AE and not the individual signs or symptoms. Symptoms and conditions present at the beginning of the study will be characterized, so that AEs can be defined as any new symptom, or any increase in frequency or severity of an existing symptom.

Following questioning and evaluation, all AEs, whether determined to be related or unrelated to the study drug by a medically qualified site PI or clinician (MD, DO, NP or PA), must be documented in the participant's medical records, in accordance with the investigator's normal clinical practice, and on the AE e-CRF. Each AE is evaluated for duration, severity, seriousness, and causal relationship to the study drug.

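### SAP 7.6 could add one nominal rate ratio for total adverse events, because Fisher's exact test on participants says little about overall AE burden over 12 months

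*SAP*

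**What the plan says.** SAP 7.6 sets the comparison of AEs and SAEs: "Differences for rates of AEs, SAEs or other abnormalities between groups will be assessed using Fisher's Exact tests". It does not say whether the unit is the participant or the event, and it names neither an exposure denominator nor an effect measure. MMRM is kept for vital signs and laboratory tests. A descriptive classification is also planned: "AEs and SAEs will be recorded and categorized by body system, event type, attribution, frequency, severity, and course". Protocol 12.0 is no wider: "Safety data will be analyzed using exact contingency table methods by study arms".

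Events are recorded one by one. Under Protocol 16.1, "AEs can be defined as any new symptom, or any increase in frequency or severity of an existing symptom", and "Each AE is evaluated for duration, severity, seriousness, and causal relationship to the study drug".

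The pilot in Protocol 3.8 compared mean AEs per participant: 1.44 vs 0.80 (p=0.04) at 10 IU bid, and 1.21 vs 0.80 (p=0.10) at 20 IU bid, the dose used here, which the text describes "with a similar trend for the high dose and placebo group comparison". Its Table 3 prints event numbers beside percentages of participants.

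Three other places bear on the point. SAP 3.4 allows for 15% to 25% dropout. SAP 6.2 promises p-values and 95% confidence intervals for every planned analysis. SAP 7.4 and 7.8 analyse Impel participants first, with Kurve-only and pooled analyses in support.

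**The concern.** SAP 7.6 sets out to assess safety and tolerability over 12 months. An any-AE comparison counts a participant with one event and a participant with six alike. In the pilot 57% to 72% of participants already had an AE within 4 months. Over 12 months most participants in both arms probably will, and the binary measure loses contrast. Dropout will also make follow-up unequal, which a participant-level Fisher test ignores. A moderate rise in the number of AEs could therefore leave little trace in the one planned between-arm comparison of overall AE frequency. At stake is how well tolerability is described. No efficacy result, sample size or stated safety decision rule depends on it.

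**Working it through.** **1. Reproduce the pilot table (Protocol 3.8, Table 3).** Participants with any AE: 17/30 = 56.7%, 26/36 = 72.2%, 26/38 = 68.4%, as printed. Events: 27, 55 and 51.

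**2. Two measures on the same pilot arms.**
- Any AE, two-sided Fisher: 10 IU bid p=0.21; 20 IU bid p=0.45.
- Event rate ratio: 10 IU bid (55/36)/(27/30) = 1.70 (95% CI 1.07 to 2.69); 20 IU bid (51/38)/(27/30) = 1.49 (0.94 to 2.38). Both intervals assume independent events. From the stated means and standard errors, the 20 IU bid ratio is 1.51 (0.83 to 2.75).
- Source of the excess at 20 IU bid: in total 51 − 38×0.90 = 16.8 events. The row labelled Other gives 33 − 38×16/30 = 12.7 of these (76%). Without that row the ratio is (18/38)/(11/30) = 1.29 (0.61 to 2.74).
- The printed means differ from events divided by participants (0.80 vs 0.90; 1.21 vs 1.34), perhaps through adjustment.

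**3. Why the unit is worth stating.** Pilot nose bleed at 10 IU bid was 6 events in 3 of 36 participants, against none of 30. Fisher gives p=0.24 on participants and p=0.028 if events are entered as if they were participants. Only the first is valid.

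**4. Illustrative power at 120 to 150 per arm.** Assumed: negative binomial counts with dispersion k from 0.25 to 1.5, no dropout, and everyone in one analysis. Twelve-month means per participant start from the pilot means:
- (a) pilot rates throughout: 3×0.80 = 2.40 vs 3×1.21 = 3.63
- (b) ratio 1.29 throughout: 2.40 vs 3.10
- (c) excess in the first 4 months only: 2.40 vs 1.21 + 0.80 + 0.80 = 2.81 (ratio 1.17)

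P(any AE) = 1 − (1 + k·m)^(−1/k). For placebo this is 84.7% at k=0.25 and 63.8% at k=1.5. SE of the log rate ratio = √[(1/m₀ + k)/n + (1/m₁ + k)/n].

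Example: (a), k=0.5, n=120. Any AE is 79.3% vs 87.4%, and exact Fisher power is 32.1%. Log ratio = 0.414 and SE = √[(0.917 + 0.775)/120] = 0.119. Power = Φ(0.414/0.119 − 1.96), about 94%, matching 94.4% by simulation.

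| Scenario | Fisher, any AE | Categories 0/1/2/3+ | Rate ratio |
|---|---|---|---|
| (a) | 19–50% | 29–90% | 66% to over 99% |
| (b) | 9–22% | 13–48% | 30–80% |
| (c) | 6–10% | 8–20% | 15–40% |

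The middle column is a test that the protocol's contingency-table wording would allow but does not specify. In (a) the 95% CI would be the estimate divided and multiplied by 1.19 to 1.41.

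**5. Stress checks.**
- With 20% dropout and a person-time denominator, 120 per arm: (a) Fisher 19–34%, robust rate ratio 64–98%; (b) 10–15% vs 31–67%. The false-positive rate of the robust test is 5–6%.
- A naive Poisson model would reject a true null with probability 2[1 − Φ(1.96/√(1 + 2.4k))] = 12% to 36%, so it should not be used.
- Less favourable: keep the pilot's 4-month risks and event rates and assume a variance/mean ratio of 3. Rate-ratio power is then 46% (n=120) and 55% (n=150), against 43% and 51% for Fisher. The pilot standard errors imply variance/mean ratios of 1.8 for placebo and 0.8 for 20 IU bid.

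**The case against.** The other side has a good deal. Fisher's test on participants with an event is valid and standard. Severity, attribution, discontinuation and DSMB review already cover other parts of AE burden, and confidence intervals are already promised in SAP 6.2, so only the measure would be new. Single AE types are reasonably served: for rhinitis at pilot size (3/38 vs 1/30, 12-month risks 1 − (1−p)³ = 21.9% vs 9.7%), by-type Fisher has 69% to 80% power. Total counts mix minor events with deterioration of the primary illness, which Protocol 16.1 counts as an AE, and they depend on how about 30 sites record repeat events. All of this stands. It limits the point to an optional addition.

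The pilot contrast (p=0.45 for Fisher against the printed 0.10) is also not a clean comparison of tests. The model behind the printed value is not given, and an unadjusted t-test from the standard errors gives about 0.13. The pilot used saline placebo and another device.

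Three stronger readings are tempting. One is that the pilot shows more AEs at this trial's dose; it shows an imprecise trend, mostly from the row labelled Other. Another is that the SAP will enter event counts into Fisher's test; it leaves the unit unstated, which is not evidence of that. A third is that the safety analysis is invalid or will miss harm; the documents support only that one summary of AE burden is absent.

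**Conclusion.** This holds as a cheap improvement, not as a flaw. The planned test is valid for participants with at least one event but insensitive to overall AE burden over 12 months. In every scenario examined the rate ratio has more power than Fisher, from a wide margin at sustained pilot rates to almost none under heavy overdispersion. With an early-only excess neither method does well.

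The ranking rests on assumed 12-month rates, dispersion and time pattern. It also assumes that all 120 to 150 per arm enter one analysis; the documents do not give the Impel/Kurve split. The two measures are different quantities, the proportion affected and the number of events per unit time, so the rate ratio belongs beside Fisher's test and not in its place.

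**What to change.** In SAP 7.6:

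1. State that Fisher's test is applied to participants with at least one event, overall and by event type.
2. Add one nominal between-arm rate ratio with 95% CI for total AEs in the blinded period, from a negative binomial model or a log-linear model with robust variance, not naive Poisson. Use as offset the log of blinded in-study time, from first dose to Month 12 or last contact. In-study time suits Protocol 8.0, which encourages participants who stop treatment to keep attending through Month 12.
3. Count one event per AE e-CRF record with onset in that period.
4. Follow the SAP's device structure: Impel participants first, then the pooled sample with device and device-by-treatment terms as in SAP 7.8.
5. Treat a nasal AE rate ratio as optional, and only with terms listed in advance. The pilot basis is thin: 7 events vs 1 at 20 IU bid, three of the 7 being nose bleeds in one person.

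The cost is a few sentences and one model on data already collected. The downsides are one more unadjusted safety estimate, dependence on site recording of recurrent events, and totals that mix minor events with disease progression.

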7.7 Analysis of Biomarker and Imaging Outcomes

Secondary Aims II and III

Individuals in the INI arm will demonstrate slower rate of decline on MRI volumes and CSF biomarkers in comparison to the placebo arm.

Analysis Plan: The rate of change in MRI volumes and CSF biomarkers will be compared between the two treatment groups using a linear mixed-effect model with MRI volumes and CSF biomarkers at each time point (including baseline) as the outcome variable. The model will include fixed effects for (i) time (as a continuous variable), (ii) time-by-treatment interaction, (iii) APOE-4 genotype (Y/N), (iv) gender (v) baseline MMSE score (vi) baseline age; and participant-specific random intercepts. The model will constrain the two treatment groups to have the same mean at baseline. The hypothesis will be tested using the p-value corresponding to the mean group difference in rate of change in MRI volumes and CSF biomarkers.

7.8 Exploratory Subgroup Analyses

Secondary Aims IV

All analyses described above will be repeated on the following subgroups to explore the differential treatment effects:

- Compliance population
- Amyloid Positive (< 600pg/ml) vs Negative (\geq 600 pg/ml) based on A β 42 MSD platform.
- Number of ApoE-e4 alleles (0, 1, 2).
- ApoE-e4 carrier status (Positive vs Negative).
- Gender Male vs Female.
- Screening MMSE median split.
- Clinical Diagnosis MCI vs AD.

Supporting analysis

Two sets of analyses will be conducted as the part of the primary, secondary and subgroup analysis.

- individuals randomized to Kurve device alone
- all individuals in the study with both Impel and Kurve device. Device and device by treatment interaction are included as fixed effects in the model. If the device by treatment interaction is not significant ($p > 0.05$), only device is included as a fixed effect.

References

- [1] Liu-Seifert, Hong, Scott W. Andersen, Ilya Lipkovich, Karen C. Holdridge, and Eric Siemers. 2015. "A Novel Approach to Delayed-Start Analyses for Demonstrating Disease-Modifying Effects in Alzheimer's Disease." Edited by Rochelle E. Tractenberg. PLOS ONE 10 (3): e0119632. doi:10.1371/journal.pone.0119632.
- [2] Liu-Seifert, Hong, Eric Siemers, Karen C. Holdridge, Scott W. Andersen, Ilya Lipkovich, Christopher Carlson, Gopalan Sethuraman, Sharon Hoog, Roza Hayduk, Rachelle Doody, Paul Aisen. 2015. "Delayed-Start Analysis: Mild Alzheimer's Disease Patients in Solanezumab Trials, 3.5 Years." *Alzheimer's Dementia: Translational Research Clinical Interventions* 1 (2): 111–21. doi:10.1016/j.trci.2015.06.006.

8 Approvals

Approved by	Title	Signature	Date
[name]	Principle Investigator		
[name]	Director, ATRI		
[name]	Lead Biostatistician		

9 Revision History

Version		
Number	Date	Revision Summary
v1.0	20180205	Original
v1.1	20180607	Add a subgroup and correct typos

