#### 4.6 Rationale for Biofluids

CSF biomarkers such as CSF A $\beta$ 42, CSF A $\beta$ 40 and CSF total tau will be measured in participants agreeing to the optional lumbar puncture. Plasma biomarkers including A $\beta$ 42, and A $\beta$ 40 will be also assessed. Plasma and CSF samples obtained in this study will be banked so that other putative biomarkers (such as CSF insulin, isoprostane 8,12-iso-iPF2 $\alpha$ -VI) may be measured by qualified investigators in the future given adequate rationale and feasibility. These putative biomarkers are among the leading candidates for AD biomarker development (Turner 2003; Grossman, Farmer et al. 2005). For example, Gilman et al, report a highly significant ( $p < 0.001$ ) effect of A $\beta$  immunization (with AN1792) on CSF tau with a total sample size of only 21 (N = 11 antibody responders and 10 placebo control participants; Gilman, Koller et al. 2005).

Several previous studies suggest that response to insulin may differ according to APOE genotype. In dose response studies that acutely elevated insulin through intravenous or intranasal administration, the greatest cognitive benefit was observed for adults with AD who were not  $\epsilon$ 4 carriers (Reger, Watson et al. 2008). The current study will examine  $\epsilon$ 4 carriage as a treatment response predictor.

Although Alzheimer's disease (AD) is a degenerative brain disorder, it may also affect peripheral tissue such as peripheral blood mononuclear cells (PBMCs). It has been suggested that PBMC-associated biomarkers may provide insights into the pathogenesis of AD and be used to monitor disease diagnosis and progression (Maes, Schipper et al. 2009). Thus biochemical analysis of the effects of intranasal insulin on PBMCs may provide some insights into therapeutic mechanisms. In addition, we will be able to compare treatment-related biomarker profiles in CSF and PBMCs.

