volumes (hippocampus, entorhinal cortex) will be analyzed with a similar strategy except that only baseline and month 12 values will be used. Other CSF biomarkers will be treated similarly in exploratory analyses. To address Secondary Aims 3 and 4, the predictive ability of APOE- $\epsilon$ 4 allele carriage and CSF biomarkers will be evaluated using RE models. A model will be developed predicting longitudinal ADAS-Cog12 response. CSF A $\beta$ 42 levels and APOE- $\epsilon$ 4 allele carriage will be included as fixed main effects along with treatment, time, and treatment-by-time interaction. A fixed effect for the interaction of A $\beta$ 42 and APOE- $\epsilon$ 4 will also be included. Potential confounders evaluated as described above will also be included as main effects. RE models make use of all observed data, and the assumption is made that any missing data is missing at random. Responses will be modeled as multivariate normal. Time will be treated as continuous and coded as months from baseline visit, (i.e. months = (exam date minus baseline date)/30.5). The correlation structure for the model will be first order autoregressive. As sensitivity analyses, both GEE (generalized estimating equations) and ANCOVA modeling will be performed. As an additional secondary (sensitivity) analysis, the above RE analysis will be performed treating time as categorical; differences between the active group and placebo group at 12 months will be assessed via contrasts in the least squares means; this analysis does not assume linearity over time. Associated p-values, standard errors of the differences, and 95 percent confidence intervals for each model will be presented for all analyses.

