## **20.2 Inclusion of Women and Minorities**

There are currently no studies that definitively support or negate the existence of significant differences in response to intranasal insulin in subgroups defined by gender or ethnic background. A specific goal percentage for women and minority enrollment is not set for this study. However, we will monitor minority enrollment throughout the study and make special effort to encourage minority enrollment. Minority enrollment will be facilitated through minority outreach effort coordinated by the Recruitment and Retention group overseen by the Coordinating Center. Each site will be encouraged to employ specific efforts (e.g. media and community outreach activities) to attract appropriate minority participants to the trial. Spanish translation is available for a variety of instruments deployed in this trial. The success of minority recruitment is based on the specific efforts of each site (e.g. media and community outreach efforts) as well as the criteria for entry. This trial has been designed to maximize minority participation in both ways. No participant will be excluded due to his or her sex, race, or ethnic group.

No studies have been completed that examine racial or ethnic differences in response to treatment with intranasal insulin. One study has been published examining gender differences in which 32 healthy participants were administered 160 IU regular human insulin or placebo intranasally; acute effects on cognitive performance were examined as outcomes. Their findings indicated that women showed the most cognitive benefit on hippocampal-dependent measures, and no sex differences on hippocampal-independent tasks (Benedict, Kern et al. 2008). Although this one study provides only modest support for sex differences, the current study will conduct secondary analyses designed to detect significant differences in intervention effect between sexes.

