3.2.2 Secondary Aims

1. To test the hypothesis that 12 months of treatment with INI (compared to placebo) in adults with aMCI or probable mild AD will improve performance on a memory composite (Story Recall and FCSRT) and on daily function in adults with aMCI and probable mild AD.
2. To test the hypothesis that INI treatment reduces the rate of hippocampal and entorhinal atrophy as measured by MRI, and conduct exploratory analyses of other brain regions.
3. To test the hypothesis that INI will favorably alter CSF $A\beta$ and the CSF $A\beta$ /tau ratio, and will modulate inflammatory markers.
4. To examine whether baseline AD biomarker profile, APOE4 allele carriage and gender predict treatment response.
5. To determine whether further improvement occurs after 18 months of treatment.

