6.2 Multiple-testing Strategy

We propose a multiple-testing strategy using a basic serial gatekeeping procedure to maintain over-all experiment-wise Type I error at $\alpha = 0.05$ (two-sided). The four hypotheses regarding (i) ADAS-Cog12, (ii) CDR-SB, (iii) memory composite (Immediate Paragraph Recall, Delayed Paragraph Recall and FCSRT), (iv) ADCS-ADL MCI will be tested in order using a basic serial testing strategy. If, for example, $p_{ADAS} \geq 0.05$, no subsequent hypotheses will be declared statistically significant. Otherwise if $p_{ADAS} < 0.05$, the CDR-SB hypothesis is tested by comparing p_{CDR} to 0.05. This strategy continues until a p -value is ≥ 0.05 , or the ADCS-ADL MCI hypothesis is declared statistically significant with $p_{ADL} < 0.05$.

Regardless of the outcome of the multiple testing strategy, p -values and 95% confidence intervals will be reported for all planned analyses.

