7.4 Analysis of Primary outcome

Individuals in the active arm with Impel device will demonstrate slower rate of decline on ADAS-Cog12 in comparison to the placebo arm. Mixed Model repeated measures analysis of variance (MMRM) will be used to assess the difference between treatment groups in change from baseline for performance on the ADAS-Cog12. Participants will be included in the model if they have both a baseline and at least one post-baseline ADAS-Cog12. Change from baseline at each post-baseline visit for the ADAS-Cog12 will be the dependent variable. We will use a heterogeneous autoregressive AR(1) covariance structure. If the heterogeneous AR(1) covariance structure results in a lack of convergence, the following covariance structures will be used in sequence: heterogeneous compound symmetry covariance, homogeneous autoregressive AR(1) covariance, homogeneous compound symmetry covariance. Fixed effects in the model will include the following terms: (i) baseline ADAS-Cog12 score, (ii) treatment, (iii) visit, (iv) treatment-by-visit interaction, and (v) APOE- ϵ 4 genotype (Y/N) (vi) gender (vii) baseline MMSE score (viii) baseline age. Visits (baseline, month 3, month 6, month 9 and month 12) will be treated as a categorical variable. The null hypothesis is that the treatment difference between active and placebo with Impel device for the ADAS-Cog12 at month 12 is equal to zero.

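### Secondary Aim 4 asks who responds to treatment, but no planned analysis compares the treatment effect between levels of biomarker, APOE-ε4 status or gender

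*SAP*

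**What the plan says.** **The aim.** SAP 3.2.2 sets Aim 4 as "To examine whether baseline AD biomarker profile, APOE4 allele carriage and gender predict treatment response"; Protocol 1.2.4 is equivalent. Protocol 4.6 says the study will examine ε4 "carriage as a treatment response predictor". Protocol 20.2 says "the current study will conduct secondary analyses designed to detect significant differences in intervention effect between sexes".

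**The SAP's analysis.** SAP 7.8 carries the Aim IV label and states: "All analyses described above will be repeated on the following subgroups to explore the differential treatment effects". The list includes amyloid status by an Aβ42 cut of 600 pg/ml, ε4 allele count, ε4 carriage and gender. Of the models being repeated, SAP 7.4 has "ii) treatment, (iii) visit, (iv) treatment-by-visit interaction", with APOE-ε4 and gender as main-effect covariates. SAP 7.7 crosses treatment with time only.

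**The protocol's analysis.** In Protocol 12.0, Aβ42 levels and APOE-ε4 "allele carriage will be included as fixed main effects along with treatment, time, and treatment-by-time interaction", together with an Aβ42-by-APOE-ε4 term. For other covariates, "Potential confounders evaluated as described above will also be included as main effects", so gender could enter only as a screened main effect.

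**Reporting.** SAP 6.2 says p-values and "95% confidence intervals will be reported for all planned analyses".

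**The concern.** Predicting treatment response means that the treatment effect differs between levels of the predictor. The quantity of interest is a difference between two treatment effects, which needs either an interaction term or an explicit contrast between strata. Neither document specifies one for any Aim 4 factor.

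The protocol's main effects and its Aβ42-by-APOE-ε4 term describe the level of ADAS-Cog12. They do not describe how the treatment effect varies. The SAP yields a separate treatment estimate in each stratum and stops there. The same section does specify a treatment interaction for device, so the tool was available but was not applied to the aim.

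With only stratum results on the page, it is tempting to compare p-values: significant in women but not in men, say. That comparison often shows a contrast when none exists. Meanwhile the contrast that would answer the aim, including the one on sex that the protocol promises, has no prespecified form.

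**Working it through.** **Where treatment is crossed with another term**

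| Source | Treatment crossed with | Aim 4 factors enter as |
|---|---|---|
| SAP 7.4 (MMRM) | visit | APOE-ε4, gender: main effects |
| SAP 7.7 (MRI, CSF) | time | APOE-ε4, gender: main effects |
| SAP 7.8, Aim IV | nothing added | strata only |
| SAP 7.8, supporting analysis | device | not applicable |
| Protocol 12.0, Aim 4 model | time | Aβ42, APOE-ε4 and their product; gender only if screened in |

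No row crosses an Aim 4 factor with treatment.

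**Inputs.** Two-sided α 0.05 (SAP 6.2); power 0.80, SD 5.72 and dropout 0.15–0.25 (Protocol 12.1); N 240–300, allocated 1:1 (Protocol 5.1 and 15.3). The subgroup shares are assumptions.

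**The plan's own figure.** The documents give no power for Aim 4. The nearest figure is Protocol Table 5: for a difference of 2.0 at 15% dropout, 4 × (5.72 × 2.8016 / 2.0)² × (1 + 0.15/2) = 276, as printed. It reproduces as a total sample size, although the text says per arm; that is a separate matter. The SD and power inputs are confirmed.

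**Comparing stratum p-values when the effect is identical in everyone.** The overall noncentrality for 80% power is 1.960 + 0.842 = 2.8016. In a stratum holding share f, power is Φ(2.8016·√f − 1.96).

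- 50/50: Φ(0.021) = 0.508 in each half. Exactly one half significant: 2 × 0.508 × 0.492 = 0.500.
- 60/40: powers 0.583 and 0.425; discordance 0.583 × 0.575 + 0.425 × 0.417 = 0.512.
- 70/30: powers 0.650 and 0.335; discordance 0.650 × 0.665 + 0.335 × 0.350 = 0.549.
- No treatment effect: 2 × 0.05 × 0.95 = 0.095.

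For three factors, simulation (20,000 trials, 200 completers, independent 50/50 splits) gives:

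| Overall power | Discordant, one factor | Discordant, any of three | Interaction test significant, any of three |
|---|---|---|---|
| 80% | 50% | 75% | 14% |
| 30% | 28–29% | 48% | 14% |
| No effect | about 9% | 21% | 14% |

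The last column agrees with 1 − 0.95³ = 0.143. The any-of-three discordance at 80% power is below 1 − 0.5³ = 0.875 because the three splits reuse the same participants.

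**Precision of the missing contrast.** Completers per arm run from 120 × 0.75 = 90 to 150 × 0.85 = 127.5. The SE of the Month 12 difference is 5.72 × √(2/n), which is 0.85 to 0.72. At a 50/50 split the interaction SE is twice that, so the 95% CI half-width is 1.96 × 2 × SE, about 3.3 to 2.8 points.

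**Power of the missing contrast.** For an interaction as large as the detectable main effect, the noncentrality is 2.8016 × √(f(1−f)). Power is 29% at f = 0.5, 28% at 0.6 and 25% at 0.7. At N = 240 with 15% dropout and a 50/50 split, 80% power needs an interaction of 4.49 points, against 2.24 for the main effect.

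**Amyloid.** Lumbar puncture is optional, so the noncentrality is multiplied by √uptake. If uptake matched the pilot's 23 of 104 (22%), power would be about 10%. For an assumed 20–80% uptake it is 10–24%.

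**The case against.** **The aim is exploratory.** Aims 1 to 3 are worded as hypothesis tests. Aim 4 is worded as an examination, and SAP 7.8 is headed exploratory. Stratum estimates with CIs are a descriptive answer, and a reader could subtract them. That stands as a limit on severity. It does not close the gap: the difference is the object of the aim, it is not a planned output, and subtracting strata gives no answer for Aβ42 as a continuous predictor, which is how the protocol model uses it.

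**The SAP contains no rule for comparing p-values.** Correct. The ordered testing in SAP 6.2 covers four overall hypotheses and no subgroup. The discordance figures are therefore conditional on a reader or author making that comparison.

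**The sex contrast is arguably planned.** SAP 5.2 covers analyses identified in the research plan as well as in the SAP, and Protocol 20.2 identifies this one. But SAP 5.2 also requires supporting post-hoc analyses not identified in the SAP to be reported as unplanned. The status is unclear at best, and no method exists either way.

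**The 50% figure overstates amyloid.** Also correct. In a lumbar puncture subset, amyloid discordance is about 25% at 22% uptake and 41% at 50% uptake. The any-of-three figure stays between about 75% and 80%.

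**The interaction test has low power.** True. That argues for showing the contrast with its wide CI, because separate stratum p-values hide the imprecision.

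**Conclusion.** The concern holds. Aim 4 and the promise in Protocol 20.2 are about treatment-effect modification, and no stated analysis estimates or tests it for any of the three factors. The omission is clearest for sex, where the protocol comes closest to promising a test.

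The primary analysis and the ordered secondary endpoints are unaffected. The harm lies in interpretation: if stratum p-values were compared, apparent differential response would arise in up to about half of trials per factor with no true difference, against 5% for an interaction test. The 80%-power scenario is close to the worst case; at 30% power or with no effect the rates are lower, as tabulated.

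These figures assume a common effect, independent splits (not established for amyloid and APOE-ε4) and the stated subgroup shares. The ±2.8 to 3.3 point interval also assumes that all 240–300 participants enter the model. SAP 7.4 and 7.8 separate Impel from Kurve participants, and the documents do not say whether 240–300 counts both; if it does, the interval for the Impel analysis is wider.

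**What to change.** In SAP 7.8, for each Aim 4 factor:

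- Fit the primary MMRM in the full sample, adding factor, factor-by-visit, factor-by-treatment and factor-by-treatment-by-visit terms. The factors are Aβ42 (lumbar puncture subset; continuous as well as by the 600 pg/ml cut), APOE-ε4 carriage and gender.
- Report the Month 12 difference in treatment effect, with its 95% CI and p-value, as the Aim 4 result, labelled exploratory.
- Keep the within-subgroup estimates and CIs, including the split by ε4 allele count, as descriptive.
- State that differential response will not be inferred by comparing stratum p-values.
- State the expected precision: about 25–29% power for an interaction as large as the detectable main effect, and less for amyloid.

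The cost is SAP wording and a few extra model runs, with no new data, visits or participants. The continuous Aβ42 model is an addition beyond the minimum, but it matches the protocol's use of Aβ42 levels. The change supplies the right contrast; it is unlikely to settle the aim at this sample size.
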